### Liver Function Abnormalities

For patients with observed worsening of liver tests considered related to regorafenib (i.e. where no alternative cause is evident, such as post-hepatic cholestasis or disease progression), the dose modification and monitoring advice in Table 8-5 should be followed.

Regorafenib is a UGT1A1 inhibitor. Mild, indirect (unconjugated) hyperbilirubinemia may occur in patients with Gilbert’s syndrome.

Table 8-4: Dose Modification/interruption for alanine aminotransferase and/or aspartate aminotransferase increases related to study drug

Increases in ASL/ALT (per NCI-CTCAE v 4.0)	1st Occurrence	Restart	Recurrence
AST and/or ALT < 5 X ULN (<Grade 3)	Continue dosing, with weekly monitoring of liver function until transaminases return to < 3 X ULN (< Grade 1) or baseline.		
ALT and/or AST > 5 X ULN (> Grade 3)	Interrupt dosing, with weekly monitoring until transaminases return to < 3 X ULN or baseline.	If the potential benefit of reinitiating regorafenib is considered to outweigh the risk of hepatotoxicity: reduce 1 dose level and measure transaminases weekly for at least 4 weeks.	Discontinue
ALT and/or AST > 20 X ULN (> Grade 4)	Discontinue		
ALT and/or AST > 3 X ULN (> Grade 2) with concurrent bilirubin > 2 X ULN	Discontinue treatment and measure transaminases weekly until resolution. Exception: subjects with Gilbert's syndrome who develop elevated transaminases should be managed as per the recommendations outlined above for ALT/AST elevations.		

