#### **Reporting of serious adverse events**

The definition of serious adverse events (SAEs) is given in Section 11(Definitions).

Each serious adverse event must be followed up until resolution or stabilization, by submission of updated reports to the designated person. An isolated laboratory abnormality that is assigned grade 4, according to CTC definition, is not reportable as an SAE; unless the investigator assesses that the event meets standard ICH criteria for an SAE. CTC grade 4 baseline laboratory abnormalities that are part of the disease profile should not be reported as an SAE, specifically when they are allowed or not excluded by the protocol inclusion/exclusion criteria.

When required, and according to local law and regulations, serious adverse events must be reported to the Ethics Committee and Regulatory Authorities.

All serious adverse events should be reported to the Coordinating Center within 24 hours. The Coordinating Center will then inform the DSMC and Bayer and will report to the RSRB using

the “reportable event” form in the ROSS system. In the event of such an event, the investigator should refer to the Pharmacovigilance section of the contract for reporting procedures.

Non-reportable research events across all sites (including UR site) will be submitted in summary at the time of the Coordinating Center’s Continuing Review.

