## Adverse events of special safety interest

As with any new chemical entity, there is always potential for unexpected adverse events, including hypersensitivity reactions.

Based on data studies with regorafenib and from current knowledge of the pharmacological properties of other small molecule tyrosine kinase inhibitors in this drug class, as soon as there is reasonable suspicion of any of the following AEs, the investigator should immediately notify the Coordinating Center as outlined in Section 11 (Reporting of Serious Adverse Events).

Reportable adverse events include:

- Acute renal failure (NCI-CTCAE version 4.0  $\geq$  grade 3) or severe proteinuria (NCI-CTCAE version 4.0  $\geq$  grade 3)
- Interstitial lung disease
- Acute cardiac failure
- Clinically significant bleeding (NCI-CTCAE version 4.0  $\geq$  grade 3)
- Stevens-Johnson Syndrome and erythema multiforme
- Hepatic failure
- Reversible posterior leukoencephalopathy syndrome
- Gastrointestinal perforation or fistula

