## Safety Analyses

The Data Safety Monitoring Committee (DSMC) at the James P. Wilmot Cancer of the University of Rochester will review and monitor toxicity and accrual data from this trial. The committee is composed of clinical specialists with experience in oncology who have no direct relationship with the study. Information that raises any questions about participant safety will be addressed with the investigators and study team.

The DSMC will provide oversight of study progress and safety by review of accrual and adverse event data at semi-annual meetings or more frequently if concerns arise. Any adverse effects requiring expedited review per protocol will be submitted to the chair of this committee for determination as to whether further action is required. This committee will meet after 6 patients have been enrolled and received at least one cycle of therapy. If >3 of these first 6 patients have delays in treatment administration due to toxicity, accrual will be held pending review and discussion with the investigators.

The study team will record and monitor adverse event rates utilizing the University of Rochester Cancer Center Clinical Trial database. If the study has two or more of the same SAEs reported in a month or more than six of the same SAEs in six months, the DSMC will review a summary of SAEs, discuss events with study investigators and conduct a detailed review. The DSMC will determine if further action is required. A copy of the DSMC reports will always be sent to all participating sites for review and submission to their local IRB.

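### The DSMC's six-month SAE trigger adds essentially nothing to its one-month trigger, so slow accumulation of the same SAE has no predefined trigger for detailed review

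*Combined protocol and SAP*

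**What the plan says.** Section 11, Safety Analyses, gives two count triggers: "two or more of the same SAEs reported in a month or more than six of the same SAEs in six months". If either is met, "the DSMC will review a summary of SAEs, discuss events with study investigators and conduct a detailed review". The protocol does not say whether a month is a calendar month or any rolling month, and it states no operating characteristics for the rules.

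The same section gives the DSMC a standing remit, exercised "by review of accrual and adverse event data at semi-annual meetings or more frequently if concerns arise", and a separate check of treatment delays in the first six patients. Under Reporting of serious adverse events, every SAE goes to the Coordinating Center within 24 hours and from there to the DSMC.

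On liver events, Table 8-4 (Section 8, Liver Function Abnormalities) ends treatment for, among others, transaminases above 20 times the upper limit and for "ALT and/or AST > 3 X ULN (> Grade 2) with concurrent bilirubin > 2 X ULN", with an exception for Gilbert's syndrome. The SAE reporting text says: "An isolated laboratory abnormality that is assigned grade 4, according to CTC definition, is not reportable as an SAE", unless the investigator judges that ICH criteria are met. The only liver item on the list under Adverse events of special safety interest is "Hepatic failure".

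**The concern.** A second trigger with a longer window is useful only if it catches a pattern that the short window misses, namely the same SAE recurring slowly. The six-month count is set so high that the monthly rule must be met first. The plan appears to have two layers of numeric surveillance and in effect has one.

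After the check on the first six patients, these two triggers are the only numeric safety rules for the remaining 54 of 60. The same SAE recurring about once a month obliges nobody to carry out the detailed review.

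The secondary issue is that both triggers count SAEs only. A liver laboratory event serious enough to end treatment under Table 8-4 need not be an SAE, and then neither trigger nor the notification list picks it up.

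**Working it through.** The plan gives no figure for these rules, so there is none to reproduce.

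**Inputs from the protocol.** Monthly trigger: 2 or more. Six-month trigger: more than 6, so 7 or more (both Section 11, Safety Analyses). Accrual: 3-4 patients per month (Section 12, Determination of sample size). **Assumed:** Poisson occurrence at 0.5 same-type SAEs per month, a mean of 3 per half-year. The documents give no SAE rate.

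**Step 1: is the six-month rule redundant?**
- Both windows by calendar: of the 792 ways to distribute 7 events over 6 months, none leaves every month with at most one. Of the 462 ways to distribute 6 events, exactly one does (one per month).
- Both windows rolling: 7 events within six months leave 6 gaps totalling at most 6 months, so the smallest gap is at most 6/6 = 1 month.
- Calendar month with rolling six months: seven events can fall in seven different calendar months, for example from 31 January to 1 July (151 days). In simulated 18-month runs at 0.33 to 1.17 events per month, the six-month rule fired first in about 0.02% to 0.3%.

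The redundancy needs no assumption about rates. Only the size of the mixed-window exception does.

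**Step 2: what can pass without a trigger?** At most six identical SAEs in six months. Accrual over that time is 6 × 3 = 18 to 6 × 4 = 24 patients, so six events equal 6/24 = 25% to 6/18 = 33% of that number. This compares counts. It is not an incidence, because patients enrolled earlier may still be on treatment.

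**Step 3: how often do n randomly timed events avoid the monthly rule?**
- Calendar month: 6!/((6−n)! 6^n).
- Rolling month: ((7−n)/6)^n.

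| n | Calendar | Rolling |
|---|---|---|
| 3 | 0.556 | 0.296 |
| 4 | 0.278 | 0.063 |
| 5 | 0.093 | 0.004 |
| 6 | 0.015 | 0.00002 |
| 7 | 0 | 0 |

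**Step 4: half-years with no trigger, at 0.5 per month.**
- Calendar: (e^−0.5 × 1.5)^6 = 0.567.
- Rolling: weight the rolling column by Poisson(3) probabilities. For n = 0 to 5 the terms are 0.0498 + 0.1494 + 0.2240 × (5/6)² + 0.2240 × 0.296 + 0.1680 × 0.0625 + 0.1008 × 0.0041 = 0.432.

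Most of this is not a failure. With calendar months, half-years with zero to two events contribute e^−3 × (1 + 3 + 3.75) = 0.386 of the 0.567.

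**Step 5: what would a lower six-month count add?** This is the probability of reaching the count while the monthly rule stays silent, at 0.5 per month.

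| Six-month count | Calendar month | Rolling month |
|---|---|---|
| 7 or more (current) | 0 | 0 |
| 5 or more | 0.010 | 0.0004 |
| 4 or more | 0.057 | 0.0105 + 0.0004 = 0.011 |
| 3 or more | 0.18 | 0.0664 + 0.0109 = 0.077 |

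A count of 5 or 6 would differ from the present rule on paper but hardly in practice.

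**The case against.** The best defence is that the redundancy does no harm. The monthly rule is sensitive, since two identical SAEs suffice, and a looser backstop beside it removes no protection. This stands: the plan is no weaker than it would be with the monthly rule alone. The strict one-per-month pattern is also rare by chance. Among half-years with six events it has probability 1.5% with calendar months and far less with a rolling month. No figure in the documents favours any particular replacement count.

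A reader might infer that slow or laboratory-only harm escapes the DSMC. The documents do not support that:
- Every SAE is passed to the DSMC individually, so one identical SAE per month is seen event by event.
- Abnormal laboratory findings are adverse events by definition (Section 11, Definitions), and the DSMC reviews adverse event data semi-annually, or sooner if concerns arise.
- The investigator may class a liver event as an SAE, either as medically important or under the ICH exception.
- The laboratory carve-out concerns an isolated grade 4 abnormality. By its wording it does not reach a combined transaminase and bilirubin elevation, although nothing makes that combination an SAE automatically.

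The defence does not rescue the six-month rule as a working rule. The plan chose to supplement judgment with counts, and one of the two counts does no work.

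**Conclusion.** The point holds as a defect in a stated safety rule. The six-month trigger is redundant by arithmetic when both windows are calendar or both rolling, and practically so when they are mixed. Slow accumulation of up to six identical SAEs in six months has no predefined trigger for detailed review and depends on case-by-case notification, semi-annual meetings and judgment. It does not follow that such harm goes unreviewed.

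The size is modest and depends on two things the documents leave open, the SAE rate and the meaning of a month. At the assumed 0.5 per month, no trigger fires in 57% of half-years with calendar months and 43% with a rolling month. Only a small part of either figure is accumulation that a lower count would catch.

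The liver point is a secondary reporting gap and not a contradiction. Events that meet a Table 8-4 discontinuation criterion and are not classed as SAEs have no expedited route to the DSMC, but they do reach it through routine review.

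**What to change.** In Section 11, Safety Analyses, define both windows as rolling and lower the six-month count to one the monthly rule does not already cover. Any value from 3 to 6 meets that condition formally, but 3 or 4 is needed for a practical effect. With a rolling month at the assumed rate, three or more raises the share of half-years with a review from about 57% to 57 + 8 = 65%, and four or more to about 58%. With calendar months the rise is from about 43% to 61% or 49%. The choice between 3 and 4 is for the sponsor and the DSMC. The cost is a few extra DSMC reviews.

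Secondarily, add liver events that meet a Table 8-4 discontinuation criterion to the notification list under Adverse events of special safety interest, whether or not they are classed as SAEs, and state that these notices go on to the DSMC. This uses laboratory tests already drawn, costs a small number of extra notices, and leaves every treatment rule unchanged.

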## 12. Statistical Methods and Determination of Sample Size

### Statistical and analytical plans

The primary end-point is grade 3-5 toxicity incidence rates. Adverse events will be grouped by system organ class and graded using NCI CTCAE version 4.0. Descriptive statistics (counts and percentages) for grade 3 and 4 toxicity rates and all-grade skin toxicity will be assessed and evaluated in relation to CGA domains.

Relative dose intensity (dose reductions, dose delays, or inability to tolerate treatment) for regorafenib will be calculated. Specific toxicities associated with dose reductions, delays and/or early discontinuation of treatment course will be identified.

Efficacy outcomes will be response rate (RR), disease control rate (DCR), progression-free survival (PFS) and overall survival (OS). Best response will be classified per RECIST criteria into complete response (CR), partial response (PR), stable disease (SD) and progressive disease (PD). Disease control will be the combination of CR + PR + SD. Kaplan-Meier survival curves will be used to estimate median PFS and OS. All statistical tests will be conducted using SAS version 9.2 (SAS Institute Inc).

Analysis of CGA results will be descriptive and will describe mean, median and standard deviations of scores at baseline and at follow up time points. CGA deficits will be captured at baseline and follow up time points. Each domain will be evaluated individually and scores will be compared between baseline and follow up time points. Overall CGA deficits will be examined and proportion of patients who decline in more than 1 domain will be determined for each time point.

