## Synopsis

Title	Regorafenib in Adults $\geq$ 65 Years with Metastatic Colorectal Cancer: A Phase II Study
Clinical study phase	Phase II
Primary study objective	To assess grade 3-5 toxicity rates of regorafenib in older adults with implementation of focused education and support initiatives
Indication	Refractory metastatic colorectal cancer (mCRC)
Diagnosis and main criteria for inclusion	
 
1. Histologically or cytologically confirmed colorectal carcinoma
 
2. Evidence of measurable (by RECIST criteria) metastatic disease
 
3. Age 65 years or over
 
4. Progression of disease on previous therapy, deemed not a candidate for further standard therapy by treating oncologist, or patient declines other options
 
5. ECOG PS 0-1
 

Study design	Single-arm, open label Phase II study
Type of control	Historical
Number of subjects	60
Plan for statistical analysis	
Adverse events will be grouped by system organ class and graded using NCI CTCAE version 4.0. Descriptive statistics for grade 3/4 toxicity rates and all-grade skin (HFS) toxicity will be assessed. Relative dose intensity for regorafenib will be calculated.
 
Based on expected grade 3-4 toxicity rates of 40-50%, a sample size of 60 patients will give approximately 10% margin of error with 95% confidence interval.
 
Secondary outcomes for efficacy will be response rate (RR), progression-free survival (PFS) and overall survival (OS). Kaplan-Meier curves will be used to estimate median PFS and OS.

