### **Determination of sample size**

Based on data from the CORRECT trial, an anticipated grade 3-4 toxicity rate of 40-50% is expected for our study. This is slightly lower than the observed grade 3-4 toxicity rate seen among patients > 65 years in the CORRECT trial. However, we hypothesize that starting at a lower dose and instituting extensive supportive care will lower the observed toxicity rate in our patient population. Using a sample size of 60 subjects with an expected toxicity rate of 45%, we will have a 90% CI of [0.341, 0.564] and an approximate 12% margin of error. Our plan is to accrue 3-4 patients per month among the four participating sites.

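### The primary analysis does not prescribe the patient-level grade 3-5 proportion, with a confidence interval, on which the 60 patients are justified, and the plan gives two levels for that interval

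*Combined protocol and SAP*

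**What the plan says.** Section 12, Statistical and analytical plans, opens with the endpoint: "The primary end-point is grade 3-5 toxicity incidence rates". It continues: "Adverse events will be grouped by system organ class and graded using NCI CTCAE version 4.0". The method follows: "Descriptive statistics (counts and percentages) for grade 3 and 4 toxicity rates and all-grade skin toxicity will be assessed", evaluated in relation to the geriatric assessment domains. No interval, confidence level, interval method or benchmark is given for the primary endpoint.

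Section 12, Determination of sample size, works with a single rate: "an anticipated grade 3-4 toxicity rate of 40-50% is expected for our study". The precision statement is: "we will have a 90% CI of [0.341, 0.564] and an approximate 12% margin of error". The same paragraph gives the reason for expecting less toxicity than in CORRECT: "we hypothesize that starting at a lower dose and instituting extensive supportive care will lower the observed toxicity rate in our patient population".

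The Synopsis names a historical control and, under its plan for statistical analysis, states a different precision: "a sample size of 60 patients will give approximately 10% margin of error with 95% confidence interval".

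Section 11 supplies a denominator, because every subject with at least one dose is valid for the safety analysis. It does not define a numerator.

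**The concern.** The sample size rests on one quantity and the analysis text describes another. The sizing quantity is a binomial proportion of patients with an interval around it. The analysis text describes counts and percentages of grade 3 and 4 toxicity, with events grouped by organ class. Organ-class percentages cannot be added to give the share of patients with any severe event, because one patient can appear in several classes. Grade 5 events belong to the endpoint but are not in the summary sentence.

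If the primary statistic stays undefined, its numerator, grade range and interval can be chosen after the data are seen. The plan also has a comparative purpose: it names a historical control and expects a lower rate. A percentage reported without its uncertainty invites direct comparison with the CORRECT rates in Section 1. With 60 patients the interval is wide enough for that comparison to mislead.

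**Working it through.** **Inputs.** n = 60; expected rate 45% (27/60), range 40-50% (Section 12). CORRECT grade 3 or higher rates are 57% for 155 patients aged 65-74 and 66% for 38 patients aged 75 or over (Section 1, Clinical Experience). Eligibility is age 65 or over (Section 5).

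**1. Reproducing the plan's interval.** Wilson score interval with continuity correction, p = 0.45, n = 60, z = 1.645, z² = 2.706:

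- Lower: [2np + z² − 1 − z√(z² − 2 − 1/n + 4p(n(1−p) + 1))] / [2(n + z²)] = (55.706 − 1.645 × 7.867) / 125.41 = 0.341
- Upper: [2np + z² + 1 + z√(z² + 2 − 1/n + 4p(n(1−p) − 1))] / [2(n + z²)] = (57.706 + 1.645 × 7.892) / 125.41 = 0.564

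This matches Section 12. The exact (Clopper-Pearson) 90% interval is nearly the same, 0.340 to 0.564. So 60 patients are justified by the precision of one patient-level proportion.

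**2. The synopsis figure.** At 95% the simple half-width is 1.960 × √(0.45 × 0.55 / 60) = 12.6 points (12.4 at 40%, 12.7 at 50%), not about 10. A 10-point half-width at 95% needs 93 to 97 patients over that range. The two statements therefore differ in level, and only the Section 12 interval reproduces.

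**3. Why organ-class percentages do not give the rate.** Section 1 lists five grade 3 or higher event rates from CORRECT: 17, 15, 8, 8 and 7%. These alone place the share of patients with any of the five between 17% (complete overlap) and 17 + 15 + 8 + 8 + 7 = 55% (no overlap).

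**4. Benchmarks.** The plan states none. Two that follow from Section 1 are 57% (ages 65-74) and the pooled older groups, (0.57 × 155 + 0.66 × 38) / 193 = 58.8%.

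**5. What the interval would show.** Exact two-sided limits are the α/2 quantile of Beta(x, n − x + 1) and the 1 − α/2 quantile of Beta(x + 1, n − x).

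| Observed | 90% interval | 95% interval | 57% excluded? | 58.8% excluded? |
|---|---|---|---|---|
| 24/60 (40%) | 29.3-51.4% | 27.6-53.5% | both levels | both levels |
| 27/60 (45%) | 34.0-56.4% | 32.1-58.4% | 90% only | both levels |
| 30/60 (50%) | 38.7-61.3% | 36.8-63.2% | neither | neither |

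**6. Bare percentage against interval.** Suppose the true rate equals the benchmark, so that toxicity has not been lowered.

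- Benchmark 57%: the observed percentage falls below it (34/60 or fewer) with probability 53%. The 90% upper limit falls below it (27/60 or fewer) with probability 4.1%.
- Benchmark 58.8%: the corresponding figures are 52% (35/60 or fewer) and 3.9% (28/60 or fewer).

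The interval rule has a cost. If the true rate is 45%, the 90% upper limit falls below 57% with probability 55%, and below 58.8% with probability 65%.

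**The case against.** The strongest reply is that this is an estimation study. Its objective is to measure toxicity, no test or threshold is set, and descriptive reporting is coherent with that aim. The sentence about lowering toxicity explains the 40-50% planning assumption and does not set up a decision. That is fair, and it disposes of three stronger readings.

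- A reader might infer that no interval will ever be produced. The documents do not support this: Section 12 and the Synopsis both foresee one. What is missing is its place among the analysis outputs and a single level.
- A reader might infer that toxicity will be reported by organ class only. Grouping by class and summarising grade 3 and 4 rates are separate sentences. The sample-size text speaks of one rate among 60 subjects, and Section 11 gives the denominator. An overall rate is undefined, not ruled out.
- A reader might infer that the hypothesis will be judged on a bare percentage. No decision rule says so. It is a risk left open by the wording.

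The choice of comparator also matters. Taking 57% alone would suggest that the expected result cannot exclude the historical rate at 95%. That figure covers ages 65-74 only, and against the pooled 58.8% the 95% interval at 27/60 does exclude it, narrowly.

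What remains is that an estimation study still needs its estimate and interval defined. Here the unsettled level and benchmark decide the reading at the plan's own expected result.

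**Conclusion.** The point holds as a gap in specification. The analysis text does not prescribe the patient-level proportion with an interval that justifies 60 patients. The level of that interval conflicts (90% in Section 12, 95% in the Synopsis), and the grades summarised do not match the endpoint. At 27/60, exclusion of the historical rate depends on both level and benchmark; at 30/60 neither benchmark is excluded at either level.

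The figures assume 60 treated patients and exact intervals. They treat each benchmark as fixed, ignoring the sampling error in CORRECT. The 58.8% is computed here from the protocol's subgroup figures and assumes CORRECT's age mix. A different mix of patients aged 65-74 and 75 or over would move it anywhere between 57% and 66%.

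**What to change.** In Section 12, Statistical and analytical plans, state the primary analysis along these lines:

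> The primary estimate is the proportion of patients who received at least one dose of regorafenib and had at least one grade 3-5 adverse event, each patient counted once at the worst grade. It will be reported with a two-sided confidence interval by [one named method] at [one level].

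- Choose one level and use it in the Synopsis and in both parts of Section 12, with a margin of error that follows from it. The exact method is one suitable choice; a continuity-corrected Wilson interval would match the sizing figure.
- Use grade 3-5 in the analysis and sample-size text, as in the endpoint, or explain the difference.
- Keep the organ-class tables as supporting summaries.
- State the CORRECT benchmark before the data are seen, including how age is handled. Base any statement that toxicity was lower on the interval against that benchmark.

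The cost is a few sentences and a line or so of SAS code, with no new data or patients. The downside is that the conclusion will be visibly less certain: at an observed 50% the interval would not support a claim of lower toxicity against either benchmark used here.

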## 2. Study objectives

### Primary Objective

- To measure grade 3-5 toxicity of regorafenib in older adults with mCRC with implementation of focused education and support initiatives

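### The primary endpoint is grade 3-5 toxicity, but the written analysis and planning rate are grade 3-4, and 60 patients do not give the synopsis margin of about 10% at 95% confidence

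*Combined protocol and SAP*

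**What the plan says.** **Endpoint.** Three places give grade 3-5:

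- Synopsis, primary study objective: "To assess grade 3-5 toxicity rates of regorafenib in older adults".
- Section 2, Primary Objective: "To measure grade 3-5 toxicity of regorafenib in older adults with mCRC".
- Section 12, Statistical and analytical plans, first sentence: "The primary end-point is grade 3-5 toxicity incidence rates".

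**Analysis.** Two places say which severe-toxicity statistics will be produced, and both stop at grade 4:

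- Synopsis, plan for statistical analysis: "Descriptive statistics for grade 3/4 toxicity rates and all-grade skin (HFS) toxicity will be assessed".
- Section 12, two sentences after the endpoint: counts and percentages "for grade 3 and 4 toxicity rates and all-grade skin toxicity will be assessed and evaluated in relation to CGA domains".

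**Planning rate.** Both statements use grade 3-4: the synopsis, and Section 12, Determination of sample size ("an anticipated grade 3-4 toxicity rate of 40-50% is expected for our study").

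**Precision.** The synopsis says that "a sample size of 60 patients will give approximately 10% margin of error with 95% confidence interval". For the same 60 patients and a 45% rate, Section 12 gives a 90% interval of [0.341, 0.564] and a margin of about 12%.

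**The concern.** Section 11 (Intensity) defines grade 5 as a category of its own, a fatal adverse event, so a grade 3-4 rate does not contain it. No sentence in the plan prescribes a grade 3-5 summary. Two analysts working from Section 12 could therefore report different headline rates, and the choice would be made after the data are in.

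The same sentence carries the grade 3-4 limit into the evaluation against the comprehensive geriatric assessment (CGA) domains, whereas the matching secondary objective in Section 2 sets no grade limit. If the sentence is followed literally, a patient whose only severe event was fatal is left out of both.

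The second issue is the precision of this rate. Precision is the only justification given for 60 patients, and the two statements of it differ in both confidence level and margin. A reader of the synopsis would expect a tighter 95% interval than the trial can give.

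**Working it through.** **Inputs.** n = 60; planning range p = 0.40 to 0.50 (synopsis and Section 12); point value p = 0.45, that is 27/60 (Section 12).

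**1. The Section 12 interval reproduces.** The Wilson interval with continuity correction, with z = 1.645 and z² = 2.706, is

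- lower = [2np + z² − 1 − z√(z² − 2 − 1/n + 4p(n(1−p) + 1))] / [2(n + z²)] = (55.706 − 12.940) / 125.41 = 0.341
- upper = [2np + z² + 1 + z√(z² + 2 − 1/n + 4p(n(1−p) − 1))] / [2(n + z²)] = (57.706 + 12.982) / 125.41 = 0.564

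This matches the stated limits. The half-width is (0.564 − 0.341)/2 = 0.1115, about 11 points; the longer arm is 0.564 − 0.45 = 0.114. Calling it about 12% is slightly loose.

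**2. The synopsis margin does not reproduce.** The normal half-width is z√(p(1−p)/60); at p = 0.45 the standard error is √(0.2475/60) = 0.0642. Exact means Clopper-Pearson.

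| p | Normal 90% | Normal 95% | Exact 90% | Exact 95% |
|---|---|---|---|---|
| 0.40 (24/60) | 0.104 | 0.124 | 0.110 | 0.130 |
| 0.45 (27/60) | 0.106 | 0.126 | 0.112 | 0.131 |
| 0.50 (30/60) | 0.106 | 0.127 | 0.113 | 0.132 |

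The Wilson, Agresti-Coull and Jeffreys intervals, and the continuity-corrected normal and Wilson intervals, were also tried. Over all seven methods the 95% half-width runs from 12.0 points (Wilson, p = 0.40) to 13.5 (normal with continuity correction, p = 0.50). None comes near 10. Half-widths of 10.2 to 10.6 points appear only at 90%, without continuity correction, so the synopsis figure looks like a 90% margin labelled 95%. That origin is an inference.

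**3. What a 10-point margin at 95% would need.** n = 1.96² p(1−p)/0.10²:

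- p = 0.40: 92.2, so 93
- p = 0.45: 95.1, so 96
- p = 0.50: 96.04, so 97

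Exact intervals need about 100 to 104. With 60 patients and p = 0.45, a 10-point half-width corresponds to 2Φ(0.10/0.0642) − 1 = 0.88, or 88% confidence.

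**4. Effect of the grade wording.** Each patient whose only severe event is grade 5 changes the rate by 1/60 = 1.67 points. The documents give no grade 5 rate, so the counts below are assumptions. Take 27 of 60 patients with a grade 3-4 event:

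| Assumed fatal-only patients | Grade 3-4 rate | Grade 3-5 rate | Difference (points) |
|---|---|---|---|
| 0 | 45.0% | 45.0% | 0 |
| 1 | 45.0% | 46.7% | 1.7 |
| 2 | 45.0% | 48.3% | 3.3 |
| 3 | 45.0% | 50.0% | 5.0 |

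Precision hardly moves: the exact 90% half-width is 11.2 points at 27/60 and at 28/60.

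**The case against.** The strongest reply concerns the grade wording. The endpoint sentence in Section 12 names both a statistic (an incidence rate) and the grades, so the grade 3-4 sentence can be read as describing supporting tables beneath it. Section 11 also puts all safety observations in the final report, and a patient with a separate grade 3 or 4 event is counted either way. This stands as far as it goes: no data are lost, and the endpoint sentence may govern. But reporting a death somewhere is not the same as counting it in the primary rate, and the plan never says that the rate includes it.

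The planning-rate mismatch may be only a label. Pooling the age-specific rates for grade 3 or higher in Section 1 gives (307 × 0.52 + 155 × 0.57 + 38 × 0.66)/500 = 54.6%, close to the 54% that Section 4 labels grade 3/4. The authors may use the two labels interchangeably. That is plausible but not proved; if so, the remedy is a relabelling.

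Counting grade 5 also raises attribution. Section 11 (Progressive disease) has signs and symptoms of progression reported as serious adverse events, so deaths linked to progression could enter the rate. That question comes from the protocol's own grade 3-5 endpoint, and calls for a sentence on which events count.

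On precision, one can say that Section 12 holds the full statement and its interval is right. That is true, and it is the synopsis that needs correcting. The choice of interval method moves the corrected margin by only about one point.

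**Conclusion.** Both parts hold. The analysis written for the primary endpoint covers grade 3-4, the endpoint is grade 3-5, and no sentence closes the gap. The size depends on an unknown number of patients whose only severe event is fatal: 1.7 points each, possibly none, and 5.0 points if there were three. The analysis is descriptive with no success threshold, so what is affected is the definition of the headline rate and of the CGA evaluation.

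The synopsis margin is wrong on its own inputs: 12.4-12.7 points (normal) or 13.0-13.2 (exact) at 95%, against the stated 10 or so. It also conflicts with Section 12, whose 90% interval is correct. These figures assume that all 60 patients receive at least one dose. Section 6 does not replace withdrawn patients, so fewer treated patients would widen the interval.

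This should be corrected before analysis, but it does not call the sample size or the data collection into question.

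**What to change.** In the synopsis and Section 12:

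1. Define the primary estimate as the proportion of patients with at least one grade 3, 4 or 5 adverse event, by worst grade per patient, among those who took at least one dose (the safety set in Section 11).
2. Use grade 3-5 in the CGA evaluation, and state the planning rate on the same definition.
3. Report the estimate with a confidence interval at one level, named identically in both places, with the margin corrected to about 11 points at 90% or about 13 points at 95% (exact intervals).
4. Keep grade-specific and system organ class tables as supporting displays.

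Two clarifications would help, though neither is a shown error. State whether the rate counts all adverse events regardless of cause, which Sections 11 and 12 seem to intend. Label the CORRECT benchmark consistently: Section 1 calls it grade 3 or higher, while Section 4 and the sample-size text say 3/4 or 3-4.

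The cost is a wording change. Adverse events are already graded and deaths recorded, and 60 patients can stand once the margin is stated correctly.
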